After the three-week baseline period and the determination that ET does not precipitate symptoms, women will be randomized to one of three arms as follows: LY500307 at a dose of 25 mg per day, LY500307 at a dose of 75 mg per day, or matched placebo for three weeks. Once the three weeks of LY500307 or placebo treatment is completed, non-menstruating women will receive one week of Provera (5 mg/day) at the end of the trial to induce a progestin withdrawal bleed. The justification for employing two separate doses of LY500307 is that the lower dose (i.e., 25 mg) may be insufficient to effectively produce agonist effects at ER beta. Prevention of the emergence of estradiol withdrawal-induced mood symptoms at the 75 mg dose (but not the 25 mg dose) would suggest either a dose-dependent agonism at ER beta or the requirement for activation of ER alpha. The latter possibility will be examined by monitoring ER α activity at the levels of the endometrium, the pituitary (plasma LH and prolactin), and possibly hypothalamus (plasma LH³³), which will help us evaluate potential ER alpha actions accompanying the higher dose of LY500307. Of note, the 75 mg daily dose is within the safety margins established by Lilly.

After the trial, those women who were taking ET prior to the study will be re-started on their previous HT regimen unless they request to continue the withdrawal from HT under medical supervision. Outcome measures will include standardized mood and behavioral rating scales. The main comparisons in this study will be between LY500307 and placebo in women with a past history of perimenopause-related depression. Results will be analyzed by analysis of variance for mixed effects and post-hoc Bonferroni testing.

Weekly visits and daily mood ratings:

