ET (three weekly measures) and DB treatment (three weekly measures). Analyses will be performed with SAS Version 9.2 software (SAS Institute, Inc, Cary, NC), using PROC MIXED (for mixed models). For each symptom rating and blood hormone level, the predictor variables of interest, DB treatment (placebo or LY500307), will be modeled as fixed effects. The covariance pattern across time will be structured as first-order autoregressive. We will use the Kenward-Roger method for computing the degrees of freedom for tests of fixed effects.

For each of the symptom outcomes, we will perform analyses to explore the effect of DB medication in the two treatment groups. We will first examine if symptoms changed from baseline (i.e., OL ET [weeks 1-3 of the trial]) to DB treatment phase (i.e., weeks 4-6 of the trial) in any of the three randomization groups (as described above). For the second analysis, if necessary, we will include the mean of the baseline (OL ET) symptom measure (for each symptom) as a covariate and compare differences in symptom ratings across each of the three randomization groups to test for effects of DB treatment. Plasma levels of estradiol, estrone, prolactin, LH and FSH during DB treatment also will be analyzed across randomization groups. For all analyses the value of the estimator (“least square means” in SAS terminology) and associated standard error of the estimator and p values will be reported. The p values will be adjusted for multiple comparisons ($k=3-6$) by the Bonferroni method, and two-sided $P < 0.05$ will be considered statistically significant.

Clinical characteristics (tables 1-3) in women with past PMD will be compared to ensure similarity across groups and include the following measures: age, BMI, menstrual bleeding, weekly average hot-flush severity scores > 2 (minimal severity), CES-D scores > 16 (consistent with clinically significant depressive symptoms of at least moderate severity ^{1;96}), and CES-D scores > 8 and < 16 (consistent with subsyndromal depression ⁹⁷⁻⁹⁹). We will employ Fisher’s exact test for categorical variables and Student’s t-tests for continuous variables.

b. Power analysis

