Based on the results of protocol 03-M-0175 ¹² and with standardized differences of .6 to .7 (and consistent with a prior meta-analysis of estrogen's effects on depressed mood ¹⁰⁰), 10 -15 women will be required in each of the three treatment cells to achieve a power of 80% with an $\alpha = 0.05$ to detect a significant difference between LY500307 and placebo with analyses of variance with repeated measures and Bonferroni t-tests in the principal outcome measures of HRSD and CES-D scales ¹⁰¹. We intend to recruit up to 80 women for this trial through this protocol. Dropouts will be replaced. Since LY500307 has never been administered to women, there is no data available to estimate the sample size needed to evaluate safety measures. Safety measures (unblinded) including symptom inventories, clinical evaluations, laboratory results, and results of EKG of all women participating in this study will be reviewed by the DSMB.

11. Human Subjects Protection

Subject selection:

a. Subject selection will be equitable. All subjects must meet the inclusion and exclusion criteria listed in Section 4. We will select physically healthy adult female individuals. The proportion of ethnic minorities (vs. Caucasians) in the total sample will be approximately consistent with the overall U.S. population proportions. The specified age range for participants in this study (i.e., ages 45 – 65 years) was selected to match the sample selection criteria we previously employed in protocol 03-M-0175. The lower age limit was to avoid enrolling women with early menopause prior to age 45 and the upper age limit would restrict participants to those who had menopause by age 55 (and therefore not women who had menopause after age 55 years). Thus we wish to study women who experienced menopause within the more normal range between ages 45 and 55 years.

b. Justification for exclusion of children:

We will exclude children or minors because the study population is women with past

perimenopausal depression.

c. Justification for exclusion of vulnerable subjects:

Those without consent capacity are excluded because the research question can be answered by enrolling only adults who can provide their own consent and there is no direct benefit for these participants. Therefore, the risks outweigh the benefits for this population.

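### Single-step Bonferroni is valid but dominated: Holm's step-down test keeps the same 5% familywise error and gives a small gain, mainly for the second dose

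*Combined protocol and SAP*

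**What the plan says.** Section 10.a (Analysis of data/study outcomes) of the combined protocol and SAP sets the rule: "The p values will be adjusted for multiple comparisons ($k=3-6$) by the Bonferroni method", and "two-sided $P < 0.05$ will be considered statistically significant". The between-arm analysis is to "compare differences in symptom ratings across each of the three randomization groups to test for effects of DB treatment", which implies three pairwise contrasts for each outcome. Section 4.d, under the double-blinded randomization phase, repeats the method: "Results will be analyzed by analysis of variance for mixed effects and post-hoc Bonferroni testing". Section 10.b (Power analysis) assumes it as well, "with analyses of variance with repeated measures and Bonferroni t-tests".

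There are two primary scales, CES-D and HRSD, and 15 women in each of three arms. No step-down, closed or hierarchical procedure appears anywhere, and no reason is given for preferring plain Bonferroni.

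**The concern.** Plain Bonferroni holds every test to the strictest threshold, however many of the others have already been rejected. A step-down procedure relaxes the threshold after each rejection without spending more than the same 5%. In arms of 15, the result most easily lost to the one-step rule is the second one: the other dose, or the other scale.

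That matters here because the protocol interprets the pattern across doses. Section 4.d says that prevention of symptoms at 75 mg but not at 25 mg would point either to dose-dependent ER beta agonism or to a need for ER alpha. If both doses work and one misses a needlessly strict threshold, a statistical artefact could be read as mechanism.

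**Working it through.** **Inputs.** From the documents: 15 per arm, three arms, two-sided 5%, k from 3 to 6, standardized difference 0.6 to 0.7. Assumed, because the documents do not say: that the standardized difference is on the analysed scale (varied in step 5), and a correlation of 0.6 between CES-D and HRSD.

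**1. The plan's own figure.** Section 10.b states "10 -15 women will be required in each of the three treatment cells" for 80% power "with standardized differences of .6 to .7". The ordinary two-sample formula is n = 2(z₁₋α/₂ₖ + z₀.₈₀)²/d².
- k = 1: 2(1.960 + 0.842)²/0.6² gives 44; at d = 0.7, 33.
- k = 3: 2(2.394 + 0.842)²/0.6² gives 59; at d = 0.7, 43.
- k = 6: 68 and 50.

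The stated 10–15 therefore does not follow from the stated inputs alone. It can be reached with an assumed within-woman correlation. With compound symmetry, correlation 0.6, three baseline and three double-blind measures and baseline as covariate, the variance factor is 0.733 − 0.36/0.733 = 0.242, which gives 15 (d = 0.6) and 11 (d = 0.7) at k = 3. Under the planned AR(1) structure, correlations from 0.2 to 0.8 gave at least 25 and 19. The correlation is not stated, so the figure is unverifiable rather than shown to be wrong.

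**2. Why Holm dominates.** Order the p values. Bonferroni compares each with 0.05/k. Holm compares the smallest with 0.05/k, the next with 0.05/(k − 1), and so on, stopping at the first failure. Every Holm threshold is at least 0.05/k, so everything Bonferroni rejects, Holm rejects. Familywise error is at most 5% under any correlation. This holds for every k from 3 to 6.

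**3. Three contrasts on one scale, both doses effective at 0.65 SD.** Simulation with normal residuals, pooled variance and 42 df. As a rough check, 0.65 × √(15/2) = 1.78 and Φ(1.78 − 2.39) ≈ 27%; using t with 42 df lowers this to about 25%.

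| | Bonferroni | Holm | Shaffer (5% on this scale alone) |
|---|---|---|---|
| Power per dose | 25% | 27% | 30% |
| Both doses significant | 12% | 16% | 22% |
| At least one dose significant | 37.4% | 37.5% | 37.6% |
| Exactly one dose (at least one minus both) | about 25% | about 21% | about 16% |

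Familywise error for this single scale: all three methods 4.3% under the global null. With one true null, Bonferroni spends only 1.6–1.7% of its 5%, while Holm and Shaffer stay at or below 5% within simulation error.

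**4. Six tests (three contrasts on two scales).** Per-test power at 0.65 SD is about 17.5% with Bonferroni and 19.4% with Holm.

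**5. If the analysed variance is small enough to give 10–15 per arm** (factor 0.24, d = 0.6): per dose 80.1% to 83.0%, both doses 69.2% to 75.2%, six-test per-test power 71.8% to 77.0%, Bonferroni to Holm. The direction does not depend on how the planning range is read.

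**6. Shaffer's version and the two scales.** Among three pairwise contrasts, once one null is rejected at most one of the other two can be true, so both may be tested at the full level. This is valid within one scale. Run at 5% separately on CES-D and HRSD, familywise error over both scales is 7.8% under the global null and 7.0–8.6% when only 75 mg works. Holm over all six tests, or Shaffer at 2.5% per scale, stays below 5%.

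**7. The open k.** At d = 0.6 (normal approximation), power is Φ(1.643 − 2.394) = 22.6% at k = 3 and Φ(1.643 − 2.638) = 16.0% at k = 6, a loss of 6.6 points. Holm's gain at k = 3 and d = 0.6 is 22.5 − 21.0 = 1.5 points.

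**The case against.** The strongest reply is that nothing here is wrong. Bonferroni is prespecified, valid and named consistently in Sections 4.d, 10.a and 10.b, and the sample size was stated on that basis. The trial is meant to yield preliminary data. The primary question, whether LY500307 prevents symptoms at all, is barely touched: the chance of at least one significant dose is the same to within a fraction of a point. Bonferroni also comes with simple matching simultaneous intervals, and a step-down rule does not. Fixing k would recover more power than Holm does.

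Most of this stands, and it limits the size of the point. It does not favour keeping the one-step rule, because Holm costs nothing in error control or assumptions.

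Two stronger readings are tempting. A reader might infer that power per dose would rise from about 60% to 68%. Those values arise at a difference of 1.0 residual SD with Shaffer's version on one scale. The plan's range is 0.6 to 0.7, and 1.0 SD lies outside it if the range is read on the analysed scale. A reader might also infer that Shaffer's test could be run at 5% within each scale at no cost. With two primary scales that breaches the 5% level (step 6).

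**Conclusion.** The concern holds as a point of efficiency, not of validity. Plain Bonferroni controls familywise error but is dominated by Holm for any k from 3 to 6; that dominance is a theorem and rests on no assumed figure.

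The size does rest on assumptions. At 0.65 SD on the analysed scale the gain is about 2 points per dose and about 4 points for showing both doses. In the low-variance reading at d = 0.6 it is about 3 and 6 points. The benefit is fewer trials in which exactly one of two effective doses reaches significance, which is the pattern the protocol would interpret biologically.

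The documents do not support reading this as a rescue of the trial's power: on the analysed scale, power per contrast at k = 3 stays near 27% with Holm at 0.65 SD. It ranks below fixing the family of comparisons.

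**What to change.** In Sections 10.a and 4.d, replace the Bonferroni wording with: *Holm step-down, applied to the same set of k comparisons for which Bonferroni would have been used, that set being fixed before unblinding.* Section 10.a keeps the blind until all 45 women have finished, so this can still be settled without knowledge of allocation. A sample size calculated for Bonferroni remains conservative under Holm, so Section 10.b does not have to change for this reason.

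If Shaffer's version is preferred for the three pairwise contrasts, state that the 5% is shared across CES-D and HRSD, for example 2.5% per scale: 0.025/3 for the smallest p value, then 0.025 and 0.025.

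Report each difference with its unadjusted 95% confidence interval, labelled as such. Such an interval may exclude zero where the step-down test does not reject; that is the one real cost. The rest is a short wording change plus the listing of the k comparisons, with no effect on participants, visits or data.

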Secondary objectives will be to evaluate the effects of LY500307 on measures of estradiol-withdrawal-induced individual affective and behavioral symptoms (daily rating form [DRF] and VAS ratings), vasomotor symptoms, plasma hormone levels (estradiol, estrone), and menstrual bleeding. Exploratory objectives will include an examination of the effects of LY500307 on gene expression profiles in lymphoblastoid cells (LCLs) or induced pluripotent cells (IPCs) from study participants. We plan to generate patient-derived LCLs and IPCs from the women participating in this protocol to investigate both intrinsic cellular differences between women with PMD and controls as well as examining the effects of estradiol withdrawal with and without invitro exposures to an ER beta agonist. Potential differences in gene expression profiles between women with and those without past perimenopausal depression, and the corresponding effects of estradiol withdrawal on these same systems are currently being examined in collaboration with the Laboratory of Neurogenetics, NIAAA. Analyses of gene expression changes in lymphoblastoid cells will be performed by RNAseq, employing gene set enrichment analysis (GSEA), weighted

gene co-expression network analysis (WGCNA) and database for annotation, visualization, and integrative discovery (DAVID) analyses, quantitative PCR to confirm the changes identified in RNAseq, and subsequent confirmation of changes in protein expression corresponding to results of gene expression data. Additionally, we will perform whole exome and whole transcriptome sequencing (and possibly whole genome sequencing) at a later date. Finally, we will monitor the effects of LY500307 on presumed estrogen receptor alpha-related tissue effects including endometrial proliferation (by vaginal ultrasound), lipids, selected plasma proteins (e.g., sex hormone binding globulin [SHBG]), plasma LH, and plasma prolactin levels.

3. Participants

a. Description of study populations:

The screening for this protocol was initially conducted as part of protocol 88-M-0131; however, this protocol (18-M-0144) was amended to include the screening phase. Due to attrition during screening (i.e., screen failures), we will need to screen approximately 80 women in this protocol to ensure that our target enrollment is met.

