During the seven-week study, the effects of LY500307 or placebo on mood symptoms will be monitored with daily symptom rating scales and weekly clinic visits. Outcome measures include the following: Primary outcome measures: self ratings - the Center for Epidemiologic Studies-Depression Scale (CES-D)⁴⁷, observer ratings - the 17-item Hamilton Rating Scale of Depression (HRSD)⁴⁸. Secondary outcome measures: the daily symptom rating form (DRF)⁴⁹ consisting of a 14 item six point likert-type scale measuring the severity of several mood and behavior symptoms including hot flushes (completed on a daily basis at home by each participant); the Beck Depression Inventory (BDI)⁵⁰; a visual analogue scale (VAS) measuring the reported severity of 13 mood and behavioral symptoms (completed at each weekly clinic visit); and whole genome expression/exome sequencing.

During eight weekly clinic visits all women will also have blood pressure, pulse, and weight measured and will be assessed for any side effects to the prescribed medications (including specific evaluations of any complaints of calf pain or other symptoms and signs of blood clots in the legs). In addition, blood samples will be drawn via venipuncture at each of the first seven clinic visits; approximately 50 ml of blood will be collected at each draw (total = 350 ml). This blood will be analyzed for several measures such as the following: estradiol, estrone, FSH, LH, prolactin, testosterone, dihydrotestosterone, SHBG, electrolytes; glucose, CBC, renal, hepatic, thyroid and lipid functions. These measures will be employed to monitor safety parameters of LY500307 (i.e., CBC, renal, hepatic, thyroid and lipid functions), and the potential effects of LY500307 on measures of ER alpha function (see above). Blood samples for estradiol will be processed within 24 hours in the NIH Clinical Center Pathology Service and sent to a staff member not involved with patient

care in order to monitor compliance with estradiol therapy.

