b. Secondary outcome measures: the daily symptom rating form (DRF) consisting of a 14 item six point likert-type scale ⁴⁹ measuring the severity of several mood and behavior symptoms including hot flushes; the Beck Depression Inventory (BDI) ⁵⁰; and a visual analogue scale (VAS) measuring the reported severity of 13 mood and behavioral symptoms during the week prior to completion. Additionally, the relative impacts of LY500307 on ER alpha versus ER beta activity will be assessed by plasma LH, FSH, prolactin, and lipid levels, and endometrial thickness as measured by vaginal ultrasound. Finally, we plan to generate patient-derived LCLs and iPSCs from the women participating in this protocol to investigate both intrinsic cellular differences between women with PMD and controls as well as examining the effects of estradiol withdrawal with and without invitro exposures to an ER beta agonist.

10. Statistical Analysis

a. Analysis of data/study outcomes

The double blind will be broken and the randomization status of each participant will be revealed only after the completion of this study in all 45 women. Interim **blinded** analyses will be performed episodically (for example prior to the PI's Board of Scientific Counsellors) to inform ongoing scientific efforts and productivity of the Branch; however, these interim analyses will not serve as the basis for decisions to change study procedures or to terminate the study. Both study outcome measures and safety assessments will be reviewed by the DSMB.

We will first test for significant differences in mood symptoms arising during the double blind (DB) conditions compared with the open label (OL) ET (baseline) conditions in each of the three groups (i.e., women with past PMD randomized to DB LY500307 [25mg or 75mg] or placebo). Second, we will compare symptom ratings during DB treatment conditions across randomization groups (i.e., women with past PMD who were randomized to either DB LY500307 or placebo).

We will obtain six repeated measures on the same woman during two phases: baseline OL

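### The Bonferroni divisor of 3 to 6 cannot cover the 28 secondary symptom outcomes, so the plan allows item-level significance claims with uncontrolled family-wise error

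*Combined protocol and SAP*

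**What the plan says.** Section 2.b makes the effect of LY500307 on individual affective and behavioral symptoms, taken from the DRF and VAS, a secondary objective. Section 9.b describes the instruments: "the daily symptom rating form (DRF) consisting of a 14 item six point likert-type scale", and "a visual analogue scale (VAS) measuring the reported severity of 13 mood and behavioral symptoms during the week prior to completion". The BDI is listed beside them.

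Section 10.a fits a mixed model to each symptom rating, uses that symptom's own baseline mean as a covariate, and compares the three randomized groups. It opens the symptom analyses with "For each of the symptom outcomes, we will perform analyses to explore the effect of DB medication in the two treatment groups". For all analyses it reports estimates, standard errors and p values. On multiplicity it says only "The p values will be adjusted for multiple comparisons ($k=3-6$) by the Bonferroni method", followed by the two-sided 0.05 criterion for significance. What k counts is not defined.

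No section makes the DRF, VAS or BDI tests conditional on CES-D or HRSD, ranks them, or names a key symptom. Section 2.b reserves its exploratory label for laboratory work: "Exploratory objectives will include an examination of the effects of LY500307 on gene expression profiles".

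**The concern.** Three arms give three pairwise contrasts for a single outcome. Adding the three within-arm changes from open-label to double-blind treatment gives six. A divisor of 3 to 6 therefore fits the comparisons inside one outcome and leaves nothing for the number of outcomes. On any other reading, k is still at most 6.

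Followed as written, the plan would let a trial that is null on CES-D and HRSD report a statistically significant LY500307 effect on one or more named symptoms. Section 4.d already says how an effect at 75 mg but not at 25 mg would be read: dose-dependent ER beta agonism or a need for ER alpha activation. A chance finding on one item, in arms of 15 women, could feed that interpretation.

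**Working it through.** **Inputs from the documents**
- Outcomes: 14 DRF items + 13 VAS symptoms + 1 BDI score = 28 (Section 9.b). Of these, 27 are individual symptoms and one is a scale score.
- Arms: three, with 15 women each (Section 3.a).
- Rule: Bonferroni with k = 3 to 6, adjusted two-sided P < 0.05 (Section 10.a). The raw thresholds are 0.05/3 = 0.0167 and 0.05/6 = 0.0083.

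**Input assumed**
- Between-symptom correlation r within a woman. The documents give none, so it is varied from 0 to 0.7.

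**The plan's own figure.** The number of pairwise contrasts among three arms is 3 × 2 / 2 = 3. With three within-arm changes, 3 + 3 = 6. The stated k = 3-6 is reproduced by counting within one outcome. Across outcomes, the between-arm contrasts alone number 28 × 3 = 84.

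**Independent outcomes.** Let e be the chance that an inert drug gives at least one significant contrast on a single outcome. The simulation described below gives e as follows, and the chance over 28 independent outcomes is 1 − (1 − e)^28:

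| Contrasts counted | k | e | 1 − (1 − e)^28 |
|---|---|---|---|
| All three | 3 | 0.043 | 1 − 0.957^28 = 0.71 |
| All three | 6 | 0.022 | 1 − 0.978^28 = 0.46 |
| Two versus placebo | 3 | 0.0308 | 1 − 0.9692^28 = 0.58 |
| Two versus placebo | 6 | 0.0157 | 1 − 0.9843^28 = 0.36 |

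The expected number of falsely significant outcomes is 28e, whatever the correlation. It runs from 28 × 0.043 = 1.2 (three contrasts, k = 3) to 28 × 0.0157 = 0.44 (two contrasts, k = 6).

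**Correlated outcomes.** Null trials were simulated with three arms of 15, 28 equally correlated normal outcomes, and pooled-variance t tests on 42 degrees of freedom at 0.05/k. The chance of at least one false result is:

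| Event | k | r = 0 | r = 0.3 | r = 0.5 | r = 0.7 |
|---|---|---|---|---|---|
| Any of three contrasts | 3 | 0.71 | 0.60 | 0.47 | 0.32 |
| Any of three contrasts | 6 | 0.46 | 0.39 | 0.30 | 0.20 |
| Either dose vs placebo, any direction | 3 | 0.58 | 0.49 | 0.38 | 0.26 |
| Either dose vs placebo, any direction | 6 | 0.36 | 0.30 | 0.23 | 0.15 |
| Either dose better than placebo | 3 | 0.35 | 0.26 | 0.19 | 0.13 |
| Either dose better than placebo | 6 | 0.20 | not tabulated | 0.12 | 0.08 |

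Against the nominal 0.05, the drug-versus-placebo rate is 0.15/0.05 = 3 times to 0.58/0.05 = 11.6 times. The false-benefit rate is 0.08/0.05 = 1.6 times to 0.35/0.05 = 7 times.

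**Check on the remedy.** Bonferroni over all 84 contrasts (0.05/84 = 0.0006) holds the simulated family-wise error at 4.7% or below.

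**Limits.** Each woman contributes one summary value per outcome, so this is not the full repeated-measures model. Within-arm changes are left out, because estradiol withdrawal may itself move symptoms in every arm and such a change is not a false drug effect.

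**The case against.** The strongest reply is that these are secondary analyses in a 45-woman mechanistic study. Section 9.a names CES-D and HRSD as primary, Section 10.b powers the trial only on them, and Section 10.a speaks of exploring the medication effect. The Précis expects only preliminary data on efficacy, and no section draws a confirmatory claim from a single item. Leaving secondary items outside family-wise control is common in such studies. Because estimates, standard errors and p values are promised for every analysis, an isolated hit would be seen beside the nulls.

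Much of this stands, and it limits how serious the point is. It does not remove it. The exploring language covers every symptom outcome, CES-D and HRSD included, so it cannot mark the secondary items as exploratory without doing the same to the primary scales. The same section then applies a significance rule to all analyses.

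Two stronger readings should be resisted:
- A reader might infer that a false symptom finding is likely, meaning more probable than not. That holds only with k = 3 and weakly correlated symptoms: r up to about 0.4 for all three contrasts, or about 0.2 for drug versus placebo alone. With k = 6 the chance stays below one half even at r = 0. The DRF and VAS rate overlapping symptoms in the same women, so positive correlation is to be expected.
- A reader might infer that the error is always at least four times 0.05. For a false benefit over placebo it can be as low as about 1.6 times.

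It is also fair that the between-arm step is worded as conditional (to be done if necessary). The figures assume that it is run for every outcome.

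**Conclusion.** The point holds as a gap in error control for the secondary symptom family. With k = 3 or 6 and an assumed correlation of 0 to 0.7, an inert drug gives roughly a 15-60% chance of at least one falsely significant drug-versus-placebo symptom result. Counting all three arm contrasts, the chance is 20-70%; for at least one false benefit over placebo, it is 8-35%. The ranges rest on the assumed correlations, on equally correlated normal outcomes, and on between-arm tests of all 28 outcomes.

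The tests of CES-D and HRSD are not affected, and the documents do not support calling the trial's main conclusion unreliable on this ground. What is at stake is which symptom findings may be called statistically significant. The change is worth making because it is cheap and alters what the trial can claim.

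**What to change.** In Section 10.a, state that among mood and behavioral symptom outcomes the P < 0.05 rule applies only to CES-D and HRSD. Report the individual DRF and VAS symptoms as exploratory least-squares mean differences with 95% confidence intervals and no significance claim. Allow the BDI a secondary claim only after a significant primary result.

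If the sponsor wants item-level claims, the alternative is to test the whole DRF, VAS and BDI family with Holm's procedure, again only after a significant primary result. Either way, the text should say whether one or both primary scales must be significant to open the gate, since the plan names two.

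Keep the existing rule for the hormone and ER alpha markers. They serve to interpret the primary result, and limiting the rule to the two depression scales without this exception would leave them with no criterion.

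The cost is one or two sentences, with no new data or participants. The downside is that a single DRF or VAS item can no longer be called statistically significant on its own.

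### Section 10b's 80% power for 10–15 women per arm does not follow from its stated inputs; under the Section 10a analysis it holds only with baseline adjustment and favourable assumptions that are not stated.

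*Combined protocol and SAP*

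**What the plan says.** Section 10b states that "10 -15 women will be required in each of the three treatment cells to achieve a power of 80" percent at alpha 0.05 for standardized differences of 0.6–0.7, "with analyses of variance with repeated measures and Bonferroni t-tests in the principal outcome measures" (HRSD and CES-D). It cites the earlier withdrawal study, 03-M-0175, and a meta-analysis as the basis for the effect size. Sections 3a and 4a fix 15 women in each of three arms.

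Section 10a describes the analysis: "We will obtain six repeated measures on the same woman during two phases", three weekly ratings on open-label estradiol and three on double-blind treatment. It specifies a mixed model and two-sided tests. On covariance: "The covariance pattern across time will be structured as first-order autoregressive". The first analysis is within groups: "We will first examine if symptoms changed from baseline". The second compares the randomized groups, and there the adjustment is conditional: "if necessary, we will include the mean of the baseline (OL ET) symptom measure". On multiplicity: "The p values will be adjusted for multiple comparisons ($k=3-6$) by the Bonferroni method".

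The contrast is named only in general terms. Section 4d says "The main comparisons in this study will be between LY500307 and placebo", and Section 10b likewise names drug against placebo. Neither says whether each dose or the two doses pooled is meant.

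**The concern.** Fifteen per arm is small for a difference of 0.6–0.7 SD between two groups, and smaller still after a Bonferroni correction. Repeated ratings can close the gap, but by how much depends on how strongly a woman's weekly ratings correlate, in what pattern, whether her open-label ratings are used, and which SD defines the 0.6–0.7. Section 10b gives none of these, so its 80% cannot be checked.

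Readers will take the trial as having 80% power at 0.6–0.7 SD. Section 1 says how a failure to confirm the hypothesis might be read, and Section 4d how an effect at 75 mg only might be read. The weight given to either reading depends on the real power.

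**Working it through.** **1. The plan's own figure from its own inputs.** For two arms and a single measurement, n per arm = 2(z₁₋α/₂ₖ + z₀.₈)² / d², where k is the Bonferroni divisor.

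- k = 1: 2(1.960 + 0.842)² / 0.36 = 43.6, so 44 (d = 0.6); divided by 0.49 it is 32.04, so 33 (d = 0.7).
- k = 3: z = 2.394, giving 58.2 and 42.7, so 59 and 43.
- k = 6: 67.3 and 49.4, so 68 and 50.
- Pooled doses against placebo, k = 1: replace 2 by 1.5, giving 33 and 25 per arm.
- One-sided, k = 1: 35 and 26.

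None of these gives 10–15, so repeated measures must supply the whole gain.

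**2. Power under Section 10a.** Noncentrality λ = d / √(2f/15), tested against t at 1 − 0.05/(2k) with 42 df (41 with a covariate). Here f is the variance of a woman's double-blind mean, after any baseline adjustment, in units of the single-week variance. Assumptions: d in SDs of one weekly rating, one dose against placebo, k = 3. Then 80% power needs λ of about 3.36, that is f ≤ 0.240 (d = 0.6) or f ≤ 0.326 (d = 0.7).

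*(a) Three double-blind weeks, no open-label covariate.* f = (1 + 2ρ)/3 under compound symmetry, or (1 + ρ)/(3 − ρ) with optimal weights under AR(1). For ρ ≥ 0 both are smallest at ρ = 0, where f = 1/3. Then λ = 0.6/0.2108 = 2.85 and 0.7/0.2108 = 3.32, giving power of 64% and 79%. Any positive correlation lowers both.

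*(b) Open-label mean as covariate, ratings truly AR(1).* f = V − C²/V, with V = (3 + 4ρ + 2ρ²)/9 and C = (ρ + 2ρ² + 3ρ³ + 2ρ⁴ + ρ⁵)/9. The documents give no ρ; 0.3–0.8 is an assumption, and the last two rows show where 80% is reached.

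| ρ | f | Power, d = 0.6 | Power, d = 0.7 |
|---|---|---|---|
| 0.3 | 0.478 | 46% | 61% |
| 0.6 | 0.584 | 37% | 51% |
| 0.8 | 0.494 | 45% | 59% |
| 0.9 | 0.323 | 65% | 81% |
| 0.93 | 0.245 | 79% | 91% |

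So 80% needs ρ of about 0.90 (d = 0.7) to 0.93 (d = 0.6). At k = 6, power for ρ of 0.3–0.8 is 28–36% and 41–51%. Pooling the doses (30 against 15, k = 3) gives 50–76% across d = 0.6–0.7.

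*(c) Open-label mean as covariate, ratings compound-symmetric.* V = (1 + 2ρ)/3 and C = ρ.

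- ρ = 0.42: f = 0.613 − 0.176/0.613 = 0.326, giving 80% at d = 0.7.
- ρ = 0.5: f = 0.292, giving 71% and 85%.
- ρ = 0.61: f = 0.740 − 0.372/0.740 = 0.237, giving 80% at d = 0.6.

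Fitting AR(1) to such data does not remove this. Simulations of the covariate analysis, with AR(1) fitted to compound-symmetric ratings, gave 81–83% for d = 0.7 at ρ = 0.45 and 78–81% for d = 0.6 at ρ = 0.6.

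*(d) If 0.6–0.7 is already in SDs of the analysed per-woman mean.* Then f = 1 and repeated measures add nothing. λ = 0.6/0.365 = 1.64 and 0.7/0.365 = 1.92, giving power of 21% and 29%.

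**The case against.** The strongest reply is that fitting an AR(1) covariance does not make the ratings AR(1). Power depends on how ratings really correlate, and no section says. Case (c) shows that a moderate, fairly even correlation supports 15 per arm with the model fitted as planned. This stands. A reader might infer from case (b) that Section 10b conflicts with Section 10a, or that a correlation above 0.9 is required. The documents do not support that: the 0.90–0.93 thresholds hold only if the data are truly AR(1).

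A model with all six weeks as outcomes also uses the baseline. Under true AR(1), a phase-by-group model reaches 80% at about 0.83–0.88. But Section 10a describes its between-group comparison as the covariate analysis, and the covariate as conditional.

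It is also fair to say that Section 10b names drug against placebo and Bonferroni tests, and that Section 10a gives k = 3–6. What is missing is narrower: the dose contrast, the divisor used for power, the SD scale and the correlation. These may be recorded with 03-M-0175, but they are not in this document.

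A reader might further infer that a null or one-dose result can say nothing about receptor mechanism. That goes too far. Sections 1 and 4d word those readings cautiously, and Section 10a compares all three groups, which allows a direct 75 mg against 25 mg comparison. Suppose both doses work equally at 0.6–0.7 SD (covariate model, AR(1) 0.3–0.8, k = 3). Then 75 mg alone is significant in 15–16% of simulated trials, but together with a significant difference between doses in only about 0.7%.

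**Conclusion.** The concern holds in a limited form. The 10–15 per arm cannot be reproduced from the stated inputs, which give 33–44, or 43–59 at k = 3. For 15 per arm under Section 10a (weekly SD scale, each dose against placebo, k = 3), power ranges from at most 64–79% without the covariate, through 37–61% with it under AR(1) of 0.3–0.8, to 80% or more with it under compound symmetry from about 0.42 (d = 0.7) or 0.61 (d = 0.6). On the analysed-mean scale it is 21–29%. All correlations here are assumptions.

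The 80% is therefore unsupported as written and depends on baseline adjustment that the plan leaves optional. A reader might conclude that it is arithmetically impossible; case (c) shows that it is not.

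**What to change.** Keep 45 women. In Section 10b, delete the 10–15 range and restate power for the 15 per arm fixed in Sections 3a and 4a, under the Section 10a analysis. State:

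- the contrast: each dose or pooled doses against placebo;
- the Bonferroni divisor;
- the SD to which 0.6–0.7 refers;
- whether the open-label mean is a covariate, settled in advance;
- the within-woman correlation and its pattern, estimated from the 03-M-0175 data that Section 10b cites. If no estimate is available, show a range labelled as an assumption that covers both AR(1) and compound symmetry.

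Then give the resulting power or detectable difference. For example, with the covariate, k = 3, 80% power and f from the working, the detectable difference is 0.7 × √(f/0.326): about 0.85–0.94 weekly SD for AR(1) of 0.3–0.8, and about 0.66 for compound symmetry of 0.5.

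The cost is wording only, with no extra participants or visits. The stated power may become less favourable.
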